7.3.1.1. Strategy of analysis and rationale

The strategy of analysis for the present study has been developed considering the following points:

- Prevalent infections are only captured by ADI during the cross-sectional surveys performed at pre-defined timepoints throughout the study. Incident infections are captured via both ADI at cross-sectional surveys and via passive detection upon spontaneous presentation at health centers (see Section 4.2 of the protocol for case definitions of *P. falciparum* infections). Episodes of clinical malaria will be treated when diagnosed. Samples collected at cross-sectional visits in asymptomatic children will not be processed in real time and will not lead to systematic treatment.
- Vaccine efficacy against prevalent *P. falciparum* infections at the successive cross-sectional surveys is an important measure as it is not influenced by care seeking behavior and possibly less influenced by blood-stage immunity. Reducing the prevalence of blood-stage infections at successive timepoints will be a good indicator of the potential to reduce transmission as it is directly associated with the potential to infect mosquitoes.
- Vaccine efficacy against first or only episode of incident *P. falciparum* infection or against first or only episode of clinical malaria minimizes the bias related to differential acquisition of blood-stage immunity in the vaccine and Control groups, and is assumed to be the best way to assess the biological effect of the third dose fractioning and spacing.
- Vaccine efficacy against all episodes of clinical malaria is more relevant to public health but over longer time periods. There is a possibility of bias related to the fact that it will compare a Control group with frequent exposure and an intervention group with reduced exposure and a different build-up of blood-stage immunity over time, possibly influencing health seeking behaviors (hence the importance of also evaluating vaccine efficacy against prevalent infection and first or only episode).
- Considering the measures of incidence:
 - For group comparisons with identical calendar time follow-up periods, the incidence rates will be directly compared. The incremental vaccine efficacy estimate is defined as 1-Incidence Rate Ratio in each group.

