7.3.1.2. Measures of incidence (*P. falciparum* infection and clinical malaria)

First or only episode

Vaccine efficacy against first or only episode of incident *P. falciparum* infection or clinical malaria will be analyzed by Cox regression stratified by study site, and overall. The 95% CI and p-values of the vaccine efficacy estimates (1- Hazard Ratio) will be calculated from this model. Cumulative incidence graphs will be produced.

• All episodes

Vaccine efficacy against all episodes of clinical malaria will be analyzed by negative binomial regression allowing for interdependence between episodes within the same subject (non-linear mixed model with over dispersion parameter estimated from the random effect). The 95% CI and p-values of the vaccine efficacy estimates (1- Incidence Rate Ratio) will be calculated from this model. In case models do not converge or showed poor fit, alternative negative binomial models without random effects will be applied. fourteen days following an episode meeting the case definition under evaluation will be subtracted from the follow-up time. The distribution of the total number of events per subject will be tabulated by group. Results per site and overall (adjusted for site as a fixed effect) will be summarized in tables and forest plots.

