- Vaccine efficacy of R012-20 + R012-14 versus Control group over M2.5-M14 (first or only episodes, PPS).
- Incremental efficacy of Fx017-20 over M7.5-M14 versus Fx012-14 over M2.5-M9 (first or only episodes, PPS).
- Incremental efficacy of Fx017-20 over M7.5-M14 versus groups R012-20 + R012-14) over M2.5-M9 (first or only episodes, PPS).
- Incremental efficacy of Fx017-20 over M7.5-M19 versus Fx012-14 over M2.5-M14 (first or only episodes, PPS).
- Incremental efficacy of Fx017-20 over M7.5-M19 versus groups R012-20 + R012- over M2.5-M14 (first or only episodes, PPS).
- Vaccine efficacy of R012-20 + R012-14 versus Control group over D0-M14 (first or only and all episodes, ES).
- Vaccine efficacy of Fx012-14 versus Control group over D0-M14 (first or only and all episodes, ES).
- Vaccine efficacy of Fx017-20 versus Control group over D0-M14 (first or only and all episodes, ES).
- Vaccine efficacy of R012-20 versus Control group over D0-M20 (all episodes, ES).
- Vaccine efficacy of R012-14 versus Control group over D0-M20 (all episodes, ES).
- Vaccine efficacy of Fx012-14 versus Control group over D0-M20 (all episodes, ES).

204889 (Malaria-094) Statistical Analysis Plan

 Vaccine efficacy of Fx017-20 versus Control group over D0-M20 (all episodes, ES).

C) Prevalent P. falciparum infections

Prevalent *P. falciparum* infections will be assessed in the ES.

Analysis performed at Month 20:

Prevalent P. falciparum infections at each cross-sectional survey

Analysis performed at Month 32:

- Prevalent *P. falciparum* infections at each cross-sectional survey

Analysis performed at Month 50:

- Prevalent *P. falciparum* infections at each cross-sectional survey

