7.3.2. Additional considerations

7.3.2.1. All planned VE Analyses and corresponding risk periods

This section describes all VE analyses (planned in protocol and additional analyses).

For each endpoint, the time at risk will be calculated separately. The time at risk will be counted in days, and expressed as person years at risk (days/365.25). In order to avoid mathematical problems because of time equals zero when an event occurred the same day that the time at risk started, the first day counts as 1 thus the duration is calculated as (date of event or censoring – date of start follow up +1). Time at risk will end at the date of next visit minus 1 to avoid including post safety and efficacy data that may have occurred on the same day.

For endpoints evaluating all episodes where time at risk does not end when the episode meets the case definition, 14 days following the episode will be subtracted from the time at risk (day of episode + 14). If an episode is detected during a period of time not counting for the time at risk it will not be included in the analysis however a table will be presented showing the number of such episodes not included in the analysis.

Table 3 Risk periods for clinical malaria & incident infection for the exposed set

Risk Period (months)	Start of risk period (at subject level)	End of risk period (at subject level)*	Group comparisons	Clinical malaria	Incident Infection
M20 analys	es				
[0-14]	Day of first vaccination of RTS,S or	Date of Month 14 visit – 1 or drop out date	Fx017-20 vs control Fx012-14 vs control	First or only- and all episodes First or only-	First or only episode First or only
	control vaccine	from study conclusion, whichever occurs first	R012-20 +R012-14 vs control Fx012-14 Vs R012-20	and all episodes First or only- and all episodes First or only-	episode First or only episode First or only
[0-20]	Day of first vaccination of	Date of Month 20 visit – 1 or	+R012-14 Fx017-20 vs control	and all episodes All episodes	episode First or only episode
	RTS,S or control	drop out date from study	Fx012-14 vs control	All episodes	First or only episode
	vaccine	conclusion, whichever	R012-20 vs control	All episodes	First or only episode
		occurs first	R012-14 vs control	All episodes	First or only episode
			Fx012-14 Vs R012-20	All episodes	First or only episode
			Fx012-14 Vs R012-14	All episodes	First or only episode
M32 analys		Data af Marath	F-047 00	All:	LAIA

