Only subjects with a confirmed negative blood slide at the beginning of the follow-up period (defined in Table 3) will be included in the analysis. The subjects will be followed-up until either having a case, or being censored (having a missing cross-sectional visit or being a drop-out whichever occurs first).

Example: the subject A described in the previous example would have been censored at the start of month 4 and contributes (3*30.5) 92 days to the time at risk.

Risk periods for prevalent parasitemia & Gametocytemia

At month 20 there are two types of analysis that will be presented:

- First, the prevalence of parasitemia/gametocytemia will be tabulated for each group (Fx017-20, Fx012-14, R012-20, R012-14 and control) at each cross sectional visit (from M0 until M20).
 - Within gametocytes positive slides the mean male/female ratio will be tabulated by group and time point and by site.
 - Within parasitemia positives the geometric mean with will be tabulated by group and time point and by site.
- Second, an analysis with endpoint all episodes of prevalent infections within risk period [M1-M20] will be performed comparing the groups (Fx017-20, Fx012-14, R012-20, R012-14) with the control. In this analysis subjects with missing visits before the last contact date will only contribute to the time at risk at the time periods

they are not missing. See example below. The subject contributes (3*30.5) + (2*30.5) = 153 days to the time at risk.

• In both analyses described above subjects with clinical malaria (case definition 1 or 2) at start day of detection of parasitemia + subsequent 14 days will be excluded.

At month 32 and month 50 the following analyses will be performed for each group, at each cross sectional visit and by site:

- the prevalence of parasitemia/gametocytemia
- male/female ratio for gametocytes positive slides
- and geometric means for parasitemia positives

Table 4 Risk periods for clinical Malaria & incident infection for the per protocol set: Comparisons with equal calendar times

Risk Period (months)	Start of risk period (at subject level)	End of risk period (at subject level)*	Group comparisons	Clinical Malaria	Incident infection
Analyses 1	2 months post do	se 3:			
• Prima	ary objective: incr	emental efficacy of f	ractional dose versus fu	II dose	
• Seco	ndary objective: v	accine efficacy of al	l groups versus controls	;	

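### Seven incident-infection lines in SAP 7.3.1.6 B call for all-episode efficacy versus Control, in conflict with Table 3 and with the SAP's own rule that follow-up ends at the first case

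*SAP*

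**What the plan says.** **The list.** SAP 7.3.1.6 B gives the incident-infection analyses for the first interim. Over Day 0 to Month 14, three lines compare RTS,S schedules with Control on both bases, for example "Vaccine efficacy of R012-20 + R012-14 versus Control group over D0-M14 (first or only and all episodes, ES". Over Day 0 to Month 20, four lines, one per RTS,S group, ask for all episodes alone: "Vaccine efficacy of R012-20 versus Control group over D0-M20 (all episodes, ES".

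**The table.** SAP 7.3.2.1 opens with "This section describes all VE analyses (planned in protocol and additional analyses". Its Table 3 has one column for clinical malaria and one for incident infection. The Month 20 row for the standard schedule reads "R012-20 vs control All episodes First or only episode", so all episodes belongs to clinical malaria and first or only to infection.

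**The rules.** SAP 7.3.1.2 states: "Vaccine efficacy against all episodes of clinical malaria will be analyzed by negative binomial regression". Infection is not mentioned there. For incident infection, 7.3.2.1 requires "Only subjects with a confirmed negative blood slide at the beginning of the follow-up period" and then says "The subjects will be followed-up until either having a case, or being censored".

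**The protocol.** Section 11.7.2 applies the all-episode model to both infection and clinical malaria, and section 11.7.6 B carries the same seven comparisons with all episodes.

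**Declared changes.** For incident infection, SAP section 10 declares the Month 20 time limit and some added analyses. Section 7.3.2.3 withdraws only the Month 33 and Month 50 infection analyses.

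**The concern.** Two parts of one SAP specify different estimates for the same comparisons. For Day 0 to Month 20 they share no version: the list has all episodes only, the table first or only. For Day 0 to Month 14 they agree on first or only, and the conflict is the extra all-episode estimate. In an open-label trial, whoever produces the tables could choose between them after results are known.

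The all-episode version also lacks a definition. The case definition of incident infection is any positive survey slide, or a case meeting the secondary clinical definition. A survey positive in a child without symptoms is left alone: "Samples collected at cross-sectional visits in asymptomatic children will not be processed in real time and will not lead to systematic treatment". A negative slide is needed only at the start of follow-up, not between episodes. The SAP gives no means of telling a new infection from one that has persisted.

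**Working it through.** **1. The lists side by side (exposed set, incident infection, versus Control).**

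| Window | Comparisons | 7.3.1.6 B | Table 3 |
|---|---|---|---|
| D0-M14 | pooled full dose; Fx012-14; Fx017-20 | first or only, and all | first or only |
| D0-M20 | R012-20; R012-14; Fx012-14; Fx017-20 | all only | first or only |

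That is 3 + 4 = 7 conflicting lines.

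**2. Which version the rest of the SAP supports.** The model in 7.3.1.2 covers clinical malaria only. Under the stop-at-first-case rule a second infection cannot be observed. Table 7, which lists the added infection analyses, is titled for first or only episodes. All three agree with Table 3.

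**3. Where the lines come from.** For its Month 21 analysis, protocol 11.7.6 B lists 19 infection comparisons: 15 on both bases and 4 on all episodes only. SAP 7.3.1.6 B reduces 12 of the 15 to first or only. The remaining 3 and the 4 keep the protocol's basis. The rationale in SAP 7.3.1.1 also drops infection from the protocol's sentence on all episodes. This looks like an incomplete edit.

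**4. What would happen under the 14-day rule.** The only all-episode rule, in 7.3.2.1, removes 14 days after each episode. The SAP's example for a child with two clinical episodes in ten months reproduces: 30.5 × 10 − 2 × 14 = 277 days.

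Monthly visits are allowed 21 to 35 days apart. Since 21 > 14, a child with a positive survey slide is always back at risk by the next survey. If still positive, the child meets the case definition again. An infection positive at k successive surveys would count k times, with a ceiling of 13 (M1 to M13) in the first window and 19 (M1 to M19) in the second.

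Example over D0-M20 (20 × 30.5 = 610 days), one infection positive at three surveys:

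- counted three times: (610 − 42)/365.25 = 1.555 person-years; 3/1.555 = 1.93 per year
- counted once: (610 − 14)/365.25 = 1.632 person-years; 1/1.632 = 0.61 per year

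**5. Effect on efficacy.** Inflated counts in both arms need not distort a ratio, so this was simulated over D0-M20 with 20,000 children per arm. None of the inputs below is in the documents: exponential infection durations, no treatment, no superinfection, monthly slides only.

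| Assumed setting | VE, first or only | VE, every positive slide |
|---|---|---|
| Control rate 0.5 to 2 per year, vaccine rate 0.6 times Control, equal mean duration of 1, 3 or 6 months | 38.5 to 41.5% | 33.6 to 40.4% |
| Equal rates (1 per year), mean duration 3 months in Control, 2 in vaccine | 7.9% | 26.6% |
| Equal rates (1 per year), mean duration 2 months in Control, 3 in vaccine | −7.7% | −38.8% |

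With equal durations, positive slides per run of positives were about 1.6, 3.1 and 4.9 for means of 1, 3 and 6 months, yet efficacy moved little. It moved a lot only when duration differed between arms. First or only is not wholly immune either, because a shorter infection is more easily missed between surveys.

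**The case against.** The strongest reply is that the SAP already settles the matter. Section 7.3.2.1 claims to cover every efficacy analysis, sets the risk periods and ends incident-infection follow-up at a case. The seven lines sit under 7.3.1, headed as protocol-planned analyses, and are leftover protocol text. A programmer following Table 3 would never count an infection twice. Repeat positives have their own declared place: the all-episode analysis of prevalent infections over Month 1 to Month 20.

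Much of this stands, and the recount is therefore conditional. But 7.3.1.6 is not a plain transcript of the protocol: it adds clinical malaria lines over Day 0 to Month 32, omits the later infection analyses and shortens 12 neighbouring lines. A reader cannot tell from it that these seven lapsed, and no declaration says so.

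Two stronger readings are tempting, and the documents do not support either.

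- *Each infection will be counted several times, so reported efficacy will be biased.* This requires setting aside the stop-at-first-case rule. It applies only while an infection stays slide-positive and untreated, whereas clinical episodes are treated when diagnosed. Any multiple restates an assumed duration, and a higher count in both arms is not in itself a bias in efficacy.
- *The first-or-only analysis is missing from the SAP.* It is absent from 7.3.1.6 B only for Day 0 to Month 20. Table 3 has it for all four RTS,S groups, and for Day 0 to Month 14 both places have it.

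**Conclusion.** The internal contradiction is established by the text and needs no assumption: seven listed all-episode analyses conflict with Table 3, with the model scope in 7.3.1.2 and with the follow-up rule in 7.3.2.1, and the departure from protocol 11.7.2 and 11.7.6 B is undeclared. It should be corrected before these analyses are run.

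The mixing of duration with incidence follows only if the lines are run with the 14-day rule. No figure can then be put on the effect on efficacy, because the documents give neither infection duration nor any difference between arms. On the assumptions shown, it ranges from slight to large enough to change the reading.

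The reach is limited. SAP section 8 makes these secondary comparisons descriptive. The primary clinical malaria analysis and the one secondary comparison in the testing hierarchy are untouched.

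**What to change.** In SAP 7.3.1.6 B, change the basis of the seven lines to first or only episode, exposed set, for both windows. They then match Table 3, 7.3.1.2 and the follow-up rule in 7.3.2.1. In section 10, declare that the protocol's all-episode incident-infection analyses up to Month 20 are dropped, and point to the prevalent-infection analysis over Month 1 to Month 20 for repeat positives. The cost is seven line edits and one declaration, with less programming.

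If the sponsor prefers to keep all-episode incident infection, which the protocol does specify, the SAP must define a new infection, for example by a negative slide or documented treatment in between. It must also amend 7.3.1.2, the follow-up rule in 7.3.2.1 and Table 3 to match. That costs more drafting and programming. What is required either way is that the sections agree and that any departure from the protocol is declared.

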7.3.2. Additional considerations

7.3.2.1. All planned VE Analyses and corresponding risk periods

This section describes all VE analyses (planned in protocol and additional analyses).

For each endpoint, the time at risk will be calculated separately. The time at risk will be counted in days, and expressed as person years at risk (days/365.25). In order to avoid mathematical problems because of time equals zero when an event occurred the same day that the time at risk started, the first day counts as 1 thus the duration is calculated as (date of event or censoring – date of start follow up +1). Time at risk will end at the date of next visit minus 1 to avoid including post safety and efficacy data that may have occurred on the same day.

For endpoints evaluating all episodes where time at risk does not end when the episode meets the case definition, 14 days following the episode will be subtracted from the time at risk (day of episode + 14). If an episode is detected during a period of time not counting for the time at risk it will not be included in the analysis however a table will be presented showing the number of such episodes not included in the analysis.

Table 3 Risk periods for clinical malaria & incident infection for the exposed set

Risk Period (months)	Start of risk period (at subject level)	End of risk period (at subject level)*	Group comparisons	Clinical malaria	Incident Infection
M20 analys	es				
[0-14]	Day of first vaccination of RTS,S or	Date of Month 14 visit – 1 or drop out date	Fx017-20 vs control Fx012-14 vs control	First or only- and all episodes First or only-	First or only episode First or only
	control vaccine	from study conclusion, whichever occurs first	R012-20 +R012-14 vs control Fx012-14 Vs R012-20	and all episodes First or only- and all episodes First or only-	episode First or only episode First or only
[0-20]	Day of first vaccination of	Date of Month 20 visit – 1 or	+R012-14 Fx017-20 vs control	and all episodes All episodes	episode First or only episode
	RTS,S or control	drop out date from study	Fx012-14 vs control	All episodes	First or only episode
	vaccine	conclusion, whichever	R012-20 vs control	All episodes	First or only episode
		occurs first	R012-14 vs control	All episodes	First or only episode
			Fx012-14 Vs R012-20	All episodes	First or only episode
			Fx012-14 Vs R012-14	All episodes	First or only episode
M32 analys		Data af Marath	F-047 00	All:	LAIA
[0-26]	Day of first vaccination of	Date of Month 26/32 visit – 1 or	Fx017-20 vs control Fx012-14 vs control	All episodes	NA
[0-32]	RTS,S or	drop out date		All episodes	
	control	from study	R012-20 vs control	All episodes	
	vaccine	conclusion,	R012-14 vs control	All episodes	
	Vaccino	whichever occurs first	Fx012-14 Vs R012-20 Fx012-14 Vs R012-14	All episodes All episodes	
M50 analys					
[0-38]	Day of first	Date of Month	Fx017-20 vs control	All episodes	NA
	vaccination of	38 visit – 1 or	Fx012-14 vs control	All episodes	
	RTS,S or	drop out date	R012-20 vs control	All episodes	
	control	from study	R012-14 vs control	All episodes	
	vaccine	conclusion,	Fx012-14 Vs R012-20	All episodes	
10.50		whichever occurs first	Fx012-14 Vs R012-14	All episodes	
[0-50]	Day of first	Date of Month	Fx017-20 vs control	All episodes	NA
	vaccination of	50 visit – 1 or	Fx012-14 vs control	All episodes	
	RTS,S or	drop out date	R012-20 vs control	All episodes	
	control vaccine	from study conclusion,	R012-14 vs control	All episodes	
	vaccine	whichever	Fx012-14 Vs R012-20	All episodes	
		occurs first	Fx012-14 Vs R012-14	All episodes	
		Coodio illot	Fx017-20 vs R012-14	All episodes	
			Fx017-20 vs Fx012-14	All episodes	

^{*} if visit date and last contact date are both missing then subjects will be censored at month [x] times 30.5 days post dose 1.

Clinical malaria

For endpoints evaluating the first or only clinical malaria, subjects who withdraw from the study before the study end will contribute to the time at risk computation. This will be explained with the help of the following figure. In these illustrative examples, for the sake of simplicity, it has been considered that visits were effectively conducted at exact monthly intervals.

	M1 30.5d	M2 30.5d	M3 30.5d	M4 30.5d	M5 30.5d	M6 30.5 d	M7 30.5 d	M8 30.5 d	M9 30.5 d	M10 30.5d	-negative +positive
Subject	-	-	-			-	-	+			. missing
Α							—				
Subject	-	-	-	+	-	+	-	-	-	-	
В			—		—				→		

Example: Subject A has two missed visits at month 4 and month 5, and an episode of clinical malaria at start of month 8. This subject will be considered to have an event at month 8, and therefore the time at risk will be (30.5d*7months) 214 days.

For endpoints evaluating all episodes 14 days following each episode will be subtracted from the time at risk (day of episode + 14). For subject B the time at risk will be (30.5*10 months) - (2*14 days) 277 days.

Incident infection

Only subjects with a confirmed negative blood slide at the beginning of the follow-up period (defined in Table 3) will be included in the analysis. The subjects will be followed-up until either having a case, or being censored (having a missing cross-sectional visit or being a drop-out whichever occurs first).

Example: the subject A described in the previous example would have been censored at the start of month 4 and contributes (3*30.5) 92 days to the time at risk.

Risk periods for prevalent parasitemia & Gametocytemia

At month 20 there are two types of analysis that will be presented:

- First, the prevalence of parasitemia/gametocytemia will be tabulated for each group (Fx017-20, Fx012-14, R012-20, R012-14 and control) at each cross sectional visit (from M0 until M20).
 - Within gametocytes positive slides the mean male/female ratio will be tabulated by group and time point and by site.
 - Within parasitemia positives the geometric mean with will be tabulated by group and time point and by site.
- Second, an analysis with endpoint all episodes of prevalent infections within risk period [M1-M20] will be performed comparing the groups (Fx017-20, Fx012-14, R012-20, R012-14) with the control. In this analysis subjects with missing visits before the last contact date will only contribute to the time at risk at the time periods

they are not missing. See example below. The subject contributes (3*30.5) + (2*30.5) = 153 days to the time at risk.

• In both analyses described above subjects with clinical malaria (case definition 1 or 2) at start day of detection of parasitemia + subsequent 14 days will be excluded.

At month 32 and month 50 the following analyses will be performed for each group, at each cross sectional visit and by site:

- the prevalence of parasitemia/gametocytemia
- male/female ratio for gametocytes positive slides
- and geometric means for parasitemia positives

Table 4 Risk periods for clinical Malaria & incident infection for the per protocol set: Comparisons with equal calendar times

Risk Period (months)	Start of risk period (at subject level)	End of risk period (at subject level)*	Group comparisons	Clinical Malaria	Incident infection
Analyses 1	2 months post do	se 3:			
• Prima	ary objective: incr	emental efficacy of f	ractional dose versus fu	II dose	
• Seco	ndary objective: v	accine efficacy of al	l groups versus controls	;	
[2½-14]	14 days post dose 3 of RTS,S or	Date of Month 14 visit – 1 or drop out date from	Primary objective: Fx012-14 vs R012-20 +R012-14	First or only- and all episodes	First or only episode
	control vaccine (day of dose 3	study conclusion, whichever occurs	Fx012-14 vs control	First or only- and all episodes	First or only episode
	vaccination + 14)	first	R012-20 +R012-14 vs control	First or only- and all episodes	First or only episode
-	months post dos	e 2 and 3: groups versus contro	ols		
[2½-9]	14 days post dose 3 of RTS,S or	Date of Month 9 visit – 1 or drop out date from	R012-20+ R012-14 vs Control	First or only- and all episodes	First or only episode
	control vaccine (day of dose 3 vaccination +	study conclusion, whichever occurs first	Fx012-14 vs control	First or only- and all episodes	First or only episode

204889 (Malaria-094) Statistical Analysis Plan

Risk Period (months)	Start of risk period (at subject level)	End of risk period (at subject level)*	Group comparisons	Clinical Malaria	Incident infection
[7½-14]	14 days post dose 3 of RTS,S or control vaccine (day of dose 3 vaccination + 14)	Date of Month 14 visit – 1 or drop out date from study conclusion, whichever occurs first	Fx017-20 vs control	First or only- and all episodes	First or only episode
[1-7]	Day of second vaccination of RTS,S or control vaccine	Date of Month 14 visit – 1 or drop out date from study conclusion, whichever occurs first	Fx017-20 vs control	First or only- and all episodes	First or only episode

Analyses up to 38 months after dose 3:

- incremental of fractional dose versus full dose
- vaccine efficacy of all groups versus controls

[2½-20]	14 days post dose 3 of	Date of Month 20 visit – 1 or drop	Fx012-14 vs control	All episodes	First or only episode
	RTS,S or control vaccine	out date from study conclusion,	R012-14 vs control	All episodes	First or only episode
	(day of dose 3 vaccination +	whichever occurs first	R012-20 vs control	All episodes	First or only episode
	14)		Fx012-14 vs R012-20	All episodes	First or only episode
			Fx012-14 vs R012-14	All episodes	First or only episode
			R012-20 vs R012-14	All episodes	First or only episode
[7½-19]	14 days post dose 3 of RTS,S or control vaccine (day of dose 3 vaccination + 14)	Date of Month 19 visit – 1 or drop out date from study conclusion, whichever occurs first	Fx017-20 vs control	All episodes	First or only episode
[2½-26]	14 days post	Date of Month 26/	R012-14 vs control	All episodes	NA
[2½-32]	dose 3 of	32/38/50 visit – 1	Fx012-14 vs control	All episodes	
[2½-38] [2½-50]	RTS,S or control vaccine	or drop out date from study	R012-20 vs control	All episodes	
[2/2-50]	(day of dose 3	conclusion,	Fx012-14 vs R012-20	All episodes	
	vaccination +	whichever occurs	Fx012-14 vs R012-14	All episodes	
	14)	first	R012-20 vs R012-14	All episodes	
[7½-26] [7½-32] [7½-38] [7½-50]	14 days post dose 3 of RTS,S or control vaccine (day of dose 3 vaccination + 14)	Date of Month 26/32/38/50 visit – 1 or drop out date from study conclusion, whichever occurs first	Fx017-20 vs control	All episodes	NA

Risk Period (months)	Start of risk period (at subject level)	End of risk period (at subject level)*	Group comparisons	Clinical Malaria	Incident infection
Analyses po	ost booster dose	(post dose 4, 5 and	6):		
[M14-M20]	Day of fourth RTS,S dose or	Date of Month 20 visit – 1 or drop	Fx012-14 vs R012-14	All episodes	First or only episode
	month 14 visit for control	out date from study conclusion,	R012-14 vs control	All episodes	First or only episode
		whichever occurs first	Fx012-14 vs control	All episodes	First or only episode
[M14-M26] [M26-M32]	Day of fourth/fifth/sixth	Date of Month 26/32/38/50 visit –	Fx012-14 vs R012-14	All episodes	NA
[M26-M38]	RTS,S dose or	1 or drop out date	R012-14 vs control	All episodes	
[M38-M50]	month 14/26/38 visit for control	from study conclusion, whichever occurs first	Fx012-14 vs control	All episodes	
[M20-M32]	Day of fourth	Date of Month 32	Fx017-20 vs R012-20	All episodes	NA
	RTS,S dose or month 20 visit	visit – 1 or drop out date from	Fx017-20 vs Control	All episodes	
	for control	study conclusion, whichever occurs first	R012-20 vs Control	All episodes	
[M32-M50]	Day of fifth RTS,S dose or M32 visit for control	Date of Month 50 visit – 1 or drop out date from study conclusion, whichever occurs first	Fx017-20 vs Control	All episodes	NA

^{*} if visit date and last contact date are both missing then subjects will be censored at month [x] times 30.5 days post dose 2/3/4/5/6.

Table 5 Risk periods for clinical Malaria & incident infection for the per protocol set: Comparisons with unequal calendar time

Risk Period (months)	Start of risk period (at subject level)	Stop (maximum)*	Group comparisons	Clinical Malaria	Incident infection
Analyses 6 m	onths post dose	3: fractional dose versu	s full dose		
[6.5 months post dose 3]	14 days post dose 3 of RTS,S (day of	Fx017-14: Date of Month 14-1 or drop out date from study	Fx017-20 vs Fx012-14	First or only- and all episodes	First or only episode
[M7.5-M14] [2.5-9]	dose 3 vaccination + 14)	conclusion, whichever occurs first All other groups: Date of Month 9 or drop out date from study conclusion, whichever occurs first	Fx017-20 vs R012-20 +R012- 14	First or only- and all episodes	First or only episode

204889 (Malaria-094) Statistical Analysis Plan

Risk Period (months)	Start of risk period (at subject level)	Stop (maximum)*	Group comparisons	Clinical Malaria	Incident infection
Analyses 12 i	months post dose	e 3: fractional dose vers	us full dose		
[1 year post dose 3] [M7.5-M19]	14 days post dose 3 of RTS,S (day of dose 3	R012-20: Date of Month 14-1 or drop out date from study conclusion, whichever	Fx017-20 vs Fx012-14	First or only- and all episodes	First or only episode
[M2.5-M14]	vaccination + 14)	occurs first All other groups: Date of the visit of fourth dose -1 or drop out date from study conclusion, whichever occurs first	Fx017-20 vs R012-20 +R012- 14	First or only- and all episodes	First or only episode

^{*} if visit date and last contact date are both missing then subjects will be censored at month [x] times 30.5 days post dose 3.

Clinical Malaria

The rules for calculating the risk periods are the same as for the exposed set.

Incident infection

Only subjects with a confirmed negative blood slide at the beginning of the follow-up period (defined in Table 2 and Table 3) will be included in the analysis. The subjects will be followed-up until being censored (either having a case, having a missing cross-sectional visit or being a drop-out whichever occurs first). For follow-up periods starting from M2.5 and M7.5, only subjects with a confirmed negative blood slide at M2 and M7 will be included in the analysis.

